## 2. Study objective(s):

The purpose of the study is to repeat our previous ex-vivo experiments in a real-life laparoscopic set up in a human/cadaveric model.

The primary objective will be to establish what the amount of benefit will be in using the VN+ as compared to a standard VN. We need to measure in a life-like situation what the reduction of the overshoot will be while in the hands of novices, junior residents and experts to validate the learning curve. Other secondary objectives are establishing the amount of haptic feedback of the VN+ compared to the standard VN and potential safety issues. All the practical investigations will need to take place in the ASC. Data study and technical alterations on the instruments will take place at the TU Delft.

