## 3. Methods

### 3.1 Study design, population and procedures

Study design: open randomized controlled prospective cross over cohort study

Study population: A) group of 10 novices, B) group of 10 surgical, urological or gynaecological residents, C) group of 10 experts consisting of surgeons, urologists or gynaecologists.

Study procedure: After information is given on the purpose and set up of the experiment all participants will be asked to sign an informed consent form.

A video will be shown of the working of a normal VN and of the VN+. After this a detailed video will be shown wherein all basic steps of the procedure are outlined. Then after randomization half of the group will start with a VN and the other half with the VN+. After 5 attempts the groups will switch device and repeat the procedure.

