### 3.2 Procedure and anatomical considerations

After making a small skin incision the insertion of the Veress needles will be:

- at Palmer's point which is 2-3 cm below the left costal margin in the midclavicular line.
- right below the umbilicus after lifting the skin with a clamp

A "grid" will be drawn on the skin. Guided by the grid each attempt will be in a new and unused part of the abdominal wall.

As in total 300 VN(+) insertions have to be performed we will probably need three cadavers

The anatomical region to be used will thus be the abdomen.

In order to see what depth the different needles reach and the possible anatomical structures that will be injured, we will first introduce a laparoscope in the left (or depending on the cadaver the right) lower abdominal quadrant via an open technique and establish pneumoperitoneum through this laparoscope trocar with a pressure that is as low as possible.

Then measurements will take place through recording the number of marks on the needle (previously laser engraved) that are to be seen in the abdomen. The actions will all be filmed and photographed.

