#### 4. Data collection and analysis

In all three groups the measured maximum insertion depths will be calculated in Excel and then any differences between the conventional (VN) and the modified (VN+) groups will be determined with a Mann-Whitney test (SPSS v16, SPSS inc. Chicago, IL) as the data will not be normally distributed. A p-value<0.05 will be considered significant.

All inadvertent tissue or organ damage will be determined and compared between the two types of needles and the groups using a Student T-test (SPSS v16, SPSS inc. Chicago, IL).

A questionnaire (with a Likert scale) will be used to establish the amount of haptic feedback the subjects experience with either the VN or the VN+ at the two different entry sites.

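### A randomised crossover is analysed with an unpaired Mann-Whitney test that uses neither participant nor period; both should enter the needle comparison together

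*Combined protocol and SAP*

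**What the plan says.** Section 3.1 describes an "open randomized controlled prospective cross over cohort study" in three experience groups: "A) group of 10 novices, B) group of 10 surgical, urological or gynaecological residents, C) group of 10 experts". Order is randomised so that half begin with each needle, and "After 5 attempts the groups will switch device and repeat the procedure". Each participant therefore contributes five attempts with each needle, in two blocks.

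Section 3.2 gives the total: "As in total 300 VN(+) insertions have to be performed we will probably need three cadavers".

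For the needle comparison, section 4 says that differences in maximum insertion depth "will be determined with a Mann-Whitney test (SPSS v16, SPSS inc. Chicago, IL) as the data will not be normally distributed". This is a test for two independent samples. Section 4 mentions no period, order, attempt number or participant. It does not say whether the observations are single insertions or participant means, or whether the comparison is made within each group of 10 or over all 30.

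Section 2 asks for the overshoot reduction in novices, residents and experts "to validate the learning curve". Section 4 contains no analysis of learning.

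**The concern.** The design creates two sources of precision that the test discards. Because each participant uses both needles, stable differences between participants could be removed from the comparison. Because order is randomised, a general change between the first and second block could be removed too. An unpaired test leaves both in the error.

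A change between blocks is plausible, since each person makes ten insertions, some of them as a novice. At stake is power in a small study: 10 participants per experience group, 30 in all. There is also a trap in the repair. The natural correction for an unpaired test is a paired one, and a paired test without a period term is more exposed to a block effect than the planned test on insertions.

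**Working it through.** **The plan's own figure.** 30 participants × 2 needles × 5 attempts = 300 insertions, as section 3.2 states. Five attempts at each of the two entry sites would give 600, so the five are shared over the sites in a way not described.

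**Inputs from the plan.** Two periods, order split half and half, five attempts per needle, 10 per experience group, significance at 0.05 (two-sided assumed).

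**Assumed, because the plan gives no SD, effect size, power or practice effect.** Insertion SD within participant = 1, normal errors; between-participant SD 0.5 or 1; needle effect 0.5 SD (10 participants) or 0.3 SD (30 participants); period step π = 0, 0.5 or 1 insertion SD; no variation between participants in the needle effect unless stated.

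**Step 1: error, not bias.** A participant's needle difference is δ + π or δ − π according to order. With equal numbers in the two orders the π terms cancel in the mean. With a 7:3 split in one group, (7 − 3)/10 = 0.4 of π would remain.

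**Step 2: unpaired comparison of insertions.** Half of each needle's insertions carry the step, which adds π²/4 to the variance within each needle. With no between-participant variance the inflation is 0.5²/4 = 6.3% and 1²/4 = 25%. A comparison of 50 v 50 insertions set at 80% power falls to 77.6% and 70.7%. With between-participant SD 1 it falls to 78.8% and 75.2%.

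**Step 3: period-adjusted crossover t-test.** The variance of a participant's difference of means is 2 × 1/5 = 0.4, so SD 0.632. Neither π nor the between-participant SD enters.
- n = 10: 0.5/(0.632/√10) = 2.5 on 8 df, power 59%.
- n = 30: 0.3/(0.632/√30) = 2.60 on 28 df, power 71%.

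**Step 4: paired t-test without period.** The variance of the differences becomes 0.4 + π², that is 0.40, 0.65 and 1.40. For n = 10 with π = 0 (9 df), power is 61%; it then falls as shown below.

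**Step 5: simulated power at π = 0 / 0.5 / 1.**

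| Analysis | n = 10, effect 0.5, between-participant SD 0.5 | n = 30, effect 0.3, between-participant SD 1 |
|---|---|---|
| Mann-Whitney on insertions | 60 / 58 / 51% | 42 / 38 / 36% |
| Mann-Whitney on participant means | 25 / 20 / 7% | about 3 / 2 / 1% |
| Paired t-test, no period | 61 / 39 / 7% | 72 / 49 / 11% |
| Period-adjusted crossover t-test | about 59% throughout | 71–73% |
| Rank-sum on period differences by order | 47–48% | 66–68% |

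Separate simulation runs differ by up to about 3 points; at π = 1 in the group of 10, the planned test on insertions ranged from 48% to 51%.

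**Step 6: false-positive rate.** With π = 1, no needle effect and no variation in the needle effect between participants, the Mann-Whitney test on insertions rejects in 0.3% to 3.0% of trials, so it is conservative. If the needle effect does vary between participants (SD 0.5), treating insertions as independent can instead give about 6–11% when the between-participant SD is 0 to 0.5. That comes from clustering, not from period.

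**The case against.** The strongest reply is that, for the test actually planned, period matters little. On insertions the loss is about 2 points of power at a period effect of 0.5 SD and about 5 to 10 points at 1 SD, and even order keeps the estimate unbiased. In the 30-participant setting the gap is 42% against about 72% before any period effect is added, so it comes from ignoring pairing. This stands, and it is why period belongs inside a within-participant analysis and is not a separate repair.

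A reader might infer that practice would cut power from 80% to 72% and then 49%, with the false-positive rate falling from 5% to 3% and 0.6%. Those figures hold for a paired t-test in 10 participants with an assumed 80% power, and shifts of 0.5 and 1 SD of the participant differences. The plan has no paired test and states no power. With the same shifts, a needle effect of 0.64 SD and no between-participant variance, Mann-Whitney on insertions gives 87%, 86% and 85%.

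A reader might also infer that the sponsor expects learning over the ten attempts. The learning-curve phrase in section 2 reads more naturally as a comparison across experience levels. No section predicts a change in depth within a session, and participants watch instruction videos first. Practice is plausible; its size and direction are assumptions.

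**Conclusion.** The concern holds in a limited form. The plan randomises order and has each participant use both needles, then analyses depth as two independent samples. The result is lost precision, not bias, provided order is balanced in each group analysed. Section 3.1 does not say whether the half-and-half split applies within each experience group, and the documents give no reason to expect an imbalance.

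The share due to period alone is small to moderate if the test is run on insertions, and larger in relative terms if it is run on participant means, where power is low from the start for want of pairing. The share due to ignoring participant grows with the differences between participants and can exceed the period share. All power figures depend on the assumed SDs, effects and normal errors, so they show direction and rough size and do not predict this study's power. The omission itself can be read directly from sections 3.1 and 4.

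**What to change.** In section 4, replace the Mann-Whitney test of depth with a within-participant crossover analysis:

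- Model depth with needle, period and experience group as fixed effects and participant as random effect. Add a participant-by-needle random effect, or analyse participant means per needle, so that insertions are not treated as independent.
- If a rank method is preferred because of non-normality, use a rank-sum test of the period differences between the two order groups.
- State the unit of analysis, and whether order is balanced within each experience group.
- Do not pre-test for carry-over.
- Treat any period effect reported by experience group as descriptive. Each attempt uses a new part of the abdominal wall, over two entry sites and probably three cadavers, so period may reflect site or cadaver as well as practice.

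The cost is wording and one degree of freedom: about 1 to 2 points of power with 10 participants and no period effect (61% against 59% above). The rank version costs more at that size, about 47–48% against 59%. No extra participants, insertions or cadavers are needed.

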### 3.2 Procedure and anatomical considerations

After making a small skin incision the insertion of the Veress needles will be:

- at Palmer's point which is 2-3 cm below the left costal margin in the midclavicular line.
- right below the umbilicus after lifting the skin with a clamp

A "grid" will be drawn on the skin. Guided by the grid each attempt will be in a new and unused part of the abdominal wall.

As in total 300 VN(+) insertions have to be performed we will probably need three cadavers

The anatomical region to be used will thus be the abdomen.

In order to see what depth the different needles reach and the possible anatomical structures that will be injured, we will first introduce a laparoscope in the left (or depending on the cadaver the right) lower abdominal quadrant via an open technique and establish pneumoperitoneum through this laparoscope trocar with a pressure that is as low as possible.

Then measurements will take place through recording the number of marks on the needle (previously laser engraved) that are to be seen in the abdomen. The actions will all be filmed and photographed.

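### No rule ties grid cells or entry sites to needles, so the plan does not guarantee that VN and VN+ are compared at like puncture positions

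*Combined protocol and SAP*

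**What the plan says.** Section 3.1 gives the design as "Study design: open randomized controlled prospective cross over cohort study". The participants are "A) group of 10 novices, B) group of 10 surgical, urological or gynaecological residents, C) group of 10 experts". After randomisation, half begin with the standard needle (VN) and half with the modified one (VN+); "After 5 attempts the groups will switch device and repeat the procedure".

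Section 3.2 sets two entry sites. One is "at Palmer's point which is 2-3 cm below the left costal margin in the midclavicular line". The other is immediately beneath the umbilicus, with no dimension given. As the section is written, a small skin incision precedes insertion. A grid is drawn on the skin, and "Guided by the grid each attempt will be in a new and unused part of the abdominal wall". On numbers: "As in total 300 VN(+) insertions have to be performed we will probably need three cadavers".

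The plan does not give the cell size, how far a cell may lie from the named site, the split of attempts between sites, the order in which cells are used, or which needle gets which cell. Section 4 compares insertion depth between needles with a Mann-Whitney test and tissue damage with a t-test. Neither analysis mentions cell, site, cadaver or pairing within participant. Entry site appears in Section 4 only for the haptic-feedback questionnaire.

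**The concern.** The site definition and the no-reuse rule pull against each other. Palmer's point is given as a 1 cm range on a single line, but dozens of punctures per cadaver must each find fresh wall nearby. As cells close to the site are used up, others have to lie further out, where tissue resistance and the distance to organs may differ. Both could plausibly affect how far a needle travels and what it can injure, and these are the outcomes of interest.

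Position would matter little to the needle comparison if each needle were sure to meet the same mix of cells and sites. Randomising the starting needle does not secure that alone. The study is also open, so nothing written down would stop a cell being chosen by someone who knows which needle is in use.

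**Working it through.** **Inputs.** Section 3.1: 3 groups of 10; 5 attempts with each of 2 needles; starting needle randomised half and half. Section 3.2: 300 insertions, probably 3 cadavers, 2 sites, no reuse of wall. Assumptions of this check: an even split between sites, a 1 cm width for the Palmer's point patch, and a range of cell spacings.

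**1. The plan's own total.** 30 x 5 x 2 = 300, which reproduces the stated figure. The five attempts per needle must therefore cover both sites together; five per needle at each site would give 600. Five is odd, so an even split over two sites is impossible for any participant and needle.

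**2. Density.** 300 / 3 = 100 per cadaver (150 with two cadavers, 75 with four). With an even split, 100 / 2 = 50 per site per cadaver. Any other split puts more than 50 at one site.

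**3. Space needed.** Area = 50 x spacing²; block side = √area.

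| Spacing | Area for 50 cells | Side of square block | Cells in a 1 x 1 cm patch |
|---|---|---|---|
| 2 mm | 2 cm² | 1.4 cm | 25 |
| 5 mm | 12.5 cm² | 3.5 cm | 4 |
| 10 mm | 50 cm² | 7.1 cm | 1 |
| 20 mm | 200 cm² | 14 cm | fewer than 1 |

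All 50 fit in the patch only if spacing is at most √(1/50) = 0.141 cm, about 1.4 mm. At 5 mm, 50 − 4 = 46 of the 50 fall outside it. The umbilical site has no stated size, so the same test cannot be made there.

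**4. Balance of position between needles.** Take 100 cells in one cadaver, numbered 0 to 99 in order of use, with 10 participants using 10 consecutive cells each. This simplification ignores site. A participant's second five cells lie on average 5 places after the first five.

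- Fixed sequence, starting needle split 5/5 within the cadaver: the +5s and −5s cancel, so the difference in mean cell number is 0.
- Fixed sequence, starting needle not balanced within the cadaver: SD = 5/√10 = 1.6 places (simulation also gave 1.6, with a largest value of 5).
- Cells falling to needles at random, unmatched: the variance of cell number is 100 x 101/12 = 841.7; SD of the difference = √(841.7 x (1/50 + 1/50)) = 5.8 places (simulation also gave 5.8).
- Cells chosen freely: no likely size can be given. The arithmetic limit is 74.5 − 24.5 = 50 places.
- Neighbouring cells paired, one to each needle at random: 50 pairs, each contributing ±1, so SD = 1/√50 = 0.14 places.

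These are places in the grid, not millimetres of depth. The documents give nothing that would convert one to the other.

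**The case against.** The strongest reply is that the crossover already deals with most of this. Every participant uses both needles and half start with each, so outward drift over a sequence of cells cancels on average. Step 4 bears this out: the imbalance is 0 or small if cells are used in a fixed order. That stands, but it depends on two conditions the plan does not state, namely a fixed order and balance of starting needle within each cadaver. If each cadaver served one group, a 5/5 split within the group would meet the second condition, but the plan does not say how participants are distributed over cadavers.

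Other parts of the reply also stand. Depth is read from the needle marks visible inside the abdomen, so wall thickness does not add to it directly. The grid openly discloses that punctures will spread, and spread that affects both needles alike limits generalisability rather than validity. Filming may allow some cell positions to be recovered, though no such step is planned.

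Several stronger readings are tempting and go too far:

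- A reader might infer that cells will be picked on the day by someone who knows the next needle. The plan is silent; a fixed sequence is just as consistent with its text.
- A reader might infer that the comparison is biased. The documents show only that position is not controlled.
- A reader might infer that the insertions cannot be made at the named sites at all. That depends on a cell size the plan does not give.
- A reader might expect depth results to be mislabelled as coming from Palmer's point. No depth or injury result by site is planned; only the questionnaire is tied to site.
- A reader might expect matched cells to bring a stated gain in precision, such as a halved variance. That would need between-cell and within-cell variation, and the documents give neither.

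**Conclusion.** The point holds as a recommended improvement, not as a fatal flaw. About 50 punctures per site per cadaver (three cadavers, even split) cannot all sit at Palmer's point unless spacing is about 1.4 mm or less in an assumed 1 x 1 cm patch. With a skin incision for each insertion, as Section 3.2 reads, spacing that tight does not look workable. Many punctures will therefore lie off the named point, and at 5 mm spacing most will.

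The plan does not secure balance of cells or sites between needles. Depending on how cells are used, imbalance per cadaver ranges from none, through SDs of 1.6 and 5.8 places in 100, to an amount that cannot be predicted if cells are chosen freely. The effect on depth or injury is unknown. What makes this more than a missing detail is that a better allocation method is available at almost no cost and has to be in place before the sessions.

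**What to change.** Before the sessions:

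- State the cell size and how far a cell may lie from each named site. Number the cells in each zone and pair neighbours.
- Give each participant five pairs from a random list, with one cell of each pair randomised to VN and the other to VN+. This keeps the total unchanged: 30 x 5 = 150 pairs = 300 insertions.
- Keep each pair within one site, so that a participant's two needles have the same split by site. A 3:2 split for half the participants in a cadaver and 2:3 for the other half gives, with ten per cadaver, 5 x 3 + 5 x 2 = 25 pairs, or 50 cells, per site.
- Balance starting needle within each cadaver.

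During the sessions, record cell, site and cadaver for every insertion.

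In the analysis, compare needles within participant and pair, for example by averaging the five VN minus VN+ depth differences for each participant and applying a signed-rank test to those 30 values. An unpaired Mann-Whitney test would not use the matching. Describe any site results, including the questionnaire, as for the left upper quadrant zone and the infra-umbilical zone.

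The cost is a prepared list, a few recorded items per insertion, a paired in place of an unpaired analysis, slightly slower set-up and a more modest site label. No extra insertions or cadavers are needed. Any gain in precision depends on the unknown variation between cells, so no figure should be claimed for it.

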#### 7. Ethical Considerations

If the VN+ really does make a significant difference in safety of VN insertion its use will lead to a worldwide reduction in morbidity and mortality caused by VN insertion. A pilot study in an ex-vivo animal (pig) model showed significant positive results. In order to take the step to clinical implementation experiments on human tissue are paramount.

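### About three cadavers carry all 300 insertions, but the VN v VN+ depth test ignores cadaver and nothing keeps a participant's two needle blocks in the same one

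*Combined protocol and SAP*

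**What the plan says.** Section 3.1 describes an "open randomized controlled prospective cross over cohort study" with three sets of participants: "A) group of 10 novices, B) group of 10 surgical, urological or gynaecological residents, C) group of 10 experts". Half start with each needle, and "After 5 attempts the groups will switch device and repeat the procedure".

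Section 3.2 gives the material: "As in total 300 VN(+) insertions have to be performed we will probably need three cadavers". It uses a grid so that no puncture site is used twice. That controls re-use of a site, not which cadaver is used.

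Section 4 gives the depth analysis: "any differences between the conventional (VN) and the modified (VN+) groups will be determined with a Mann-Whitney test", and "A p-value<0.05 will be considered significant". It names no cadaver stratum, model term or per-cadaver result.

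No section says how participants, experience groups or needles are spread over the cadavers, or that the cadaver is recorded with each depth. The limitations in section 6 do not mention the number of cadavers.

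**The concern.** How far a needle overshoots may depend on the abdominal wall as well as on the operator. With about 100 insertions in each of three cadavers, the study has many punctures but only three walls. Two things follow.

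- **Cadaver level may enter the needle contrast.** The crossover removes a cadaver's general depth level only if a participant uses both needles in the same cadaver. The plan does not require that. Because every attempt needs a fresh grid position, a full grid could move someone to another cadaver at the switch.
- **Variation of the benefit between abdomens goes unseen.** Even with both blocks in one cadaver, the needle difference may be larger in one abdomen than in another. One cadaver with a large difference could drive the overall result, and the planned output would not show it.

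The primary objective in section 2 is the size of the VN+ benefit, and section 7 looks towards clinical use: "In order to take the step to clinical implementation experiments on human tissue are paramount". A reader will want to apply the result to abdomens in general, and the planned p-value does not support that.

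**Working it through.** **1. The plan's own figure.** 30 participants (section 3.1) x 5 attempts x 2 needles = 300, which matches section 3.2. This holds if the five attempts per needle are shared over the two entry sites; five per site would give 600. On 300, each of three cadavers takes about 100 insertions, or 50 per needle if balanced. The documents contain no sample-size calculation to reproduce.

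**2. When cadaver level cancels.** Let m(c) be the general depth level of cadaver c. With both blocks in cadaver c, a participant's VN minus VN+ difference contains m(c) - m(c) = 0. With the blocks in cadavers c and c', it contains m(c) - m(c'). Whether this adds only noise or also bias depends on how evenly the needles fall over the cadavers, which the plan leaves open.

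**3. What remains when it cancels.** Let tau be the SD of the needle difference between cadavers. With three cadavers, its contribution to the variance of the overall difference is tau²/3. More operators or insertions in the same three cadavers do not reduce it.

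**4. Illustration in mm.** All inputs are assumptions: a participant-level analysis (which section 4 does not plan) with standard error 1.5 mm, and tau of 0, 2, 3 or 5 mm.

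Total SE = sqrt(1.5² + tau²/3). Coverage of a nominal 95% interval = 2Φ(1.96 x 1.5 / total SE) - 1.

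| tau (mm) | Total SE (mm) | Coverage |
|---|---|---|
| 0 | sqrt(2.25) = 1.50 | 95% |
| 2 | sqrt(2.25 + 1.33) = 1.89 | 88% |
| 3 | sqrt(2.25 + 3.00) = 2.29 | 80% |
| 5 | sqrt(2.25 + 8.33) = 3.25 | 63% |

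(The last SE is 3.253 unrounded, so 3.3 to one decimal.)

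**5. The planned test itself.** Suppose section 4 means one test of 150 v 150 depths. In units of the SD of one insertion, the variance taken under independence is 2/150 = 0.0133; the true variance is 0.0133 + tau²/3. Mann-Whitney was simulated (4,000 runs per setting, two-sided 5%, 50 per needle in each of three cadavers), with the average benefit zero but varying between cadavers:

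| tau (SD units, assumed) | Variance ratio | Rejection, no cadaver main effect | Rejection, cadaver main effect SD 0.5 |
|---|---|---|---|
| 0 | 1.00 | 5% | 4% |
| 0.1 | 1.25 | 8% | 6% |
| 0.2 | 2.00 | 16% | 12% |
| 0.3 | 3.25 | 26% | 23% |
| 0.5 | 7.25 | 45% | 41% |

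If section 4 means one test per experience group (50 v 50), the formula gives 9% at tau = 0.2 and 14% at 0.3 with the group spread over three cadavers, and 17% and 28% with the group confined to one. These calculations leave out clustering of attempts within operator, which is a separate matter.

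**6. How little three cadavers can say about tau.** An analysis with cadaver as the unit has 2 degrees of freedom and critical value 4.303. Its 95% half-width is 4.303 x sqrt(0.0133) = 0.50 SD even at tau = 0, against 1.96 x sqrt(0.0133) = 0.23 SD under independence.

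**The case against.** The strongest reply is that this limits scope and does not invalidate the test. If the needles do not differ in any cadaver, tau is zero and, with both blocks in one cadaver, the simulated error is about 5% or slightly below. The inflated rates need an average benefit of zero with VN+ better in some abdomens and worse in others. This stands: the plan's p-value is not shown to be wrong for the cadavers actually used.

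Four stronger readings are tempting, and the documents do not support them.

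- A reader might take section 6 as admitting that cadavers differ from one another in tissue. It compares cadavers with living tissue, so it is no evidence of variation between cadavers.
- A reader might suppose that the planned result at least covers variation between the 30 operators. Section 4 plans an independent-samples test without pairing or participant summaries, and a p-value with no interval. The coverage figures therefore describe a hypothetical, repaired analysis.
- A reader might infer that section 7 makes this p-value the trigger for clinical use. It says that work on human tissue is needed before that step and sets no such rule.
- A reader might infer that participants will change cadaver at the switch. The plan is silent; this is a possibility it leaves open.

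It is also fair that every variance input is assumed. That limits the claim about size, but not the facts that cadaver is absent from the analysis and its allocation is unspecified.

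**Conclusion.** The point holds as a limit on what the comparison can show, together with an avoidable gap in the allocation. Three facts are firm: 300 insertions in probably three cadavers, a depth test without cadaver, and no rule keeping both needle blocks in one cadaver. So cadaver differences can enter the needle contrast. Even when they do not, the p-value, and any interval built the same way, says nothing about variation of the benefit between abdomens.

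The size is unknown. It runs from nothing at tau = 0 to serious under-coverage (63%) at an assumed tau of 5 mm beside an assumed standard error of 1.5 mm. It would go too far to conclude that the comparison within these cadavers is invalid, or that the benefit is known to differ between abdomens.

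**What to change.** - **Section 3.1:** each participant makes all ten insertions in one cadaver. Spread the experience groups over the cadavers and balance starting needle within each. With three cadavers, ten participants per cadaver and each group split 4/3/3 in rotation allows five VN-first and five VN+-first in every cadaver and in every group. Set this before the experiment.
- **Data sheet:** record the cadaver with every depth. Without it, the results may not be recoverable by cadaver.
- **Section 4:** compare the needles within participant and cadaver. Report the VN minus VN+ difference for each cadaver beside the overall figure, as description and not as a test. Agreement in direction should not license a general claim: with no true effect, all three cadavers favour VN+ by chance with probability (1/2)³ = 1/8.
- **Section 6:** state that inference is limited to the roughly three cadavers used.

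The cost is a simple allocation constraint, one data column, one small table and a narrower claim. No extra cadavers or insertions are needed. The fix removes cadaver level from the contrast and makes gross disagreement visible; it cannot estimate tau well from three cadavers.
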